4.3.2 Main Analytical Approach

The treatment effect on the primary efficacy endpoint, rate of change (slope) in the area of ellipsoid zone defect ($\text{mm}^2/18$ months) measured by en face SD-OCT from Baseline through Month 18, will be estimated using a mixed model for repeated measures (MMRM). The model will include all observed area of ellipsoid zone defect at each scheduled visit from Baseline through Month 18 in the response variable. The fixed effects will include treatment group (ACP or Sham), time, pooled geographic region (North America or Rest of World), and treatment by time interaction. Time is defined as a continuous variable in number of study days since randomization (calculated as: visit date – randomization date + 1). The model will include an unstructured modeling of within-participant correlations, induced by random effects at the participant-level. The MMRM model will be fitted using restricted maximum likelihood (REML) estimation. If this analysis fails to converge, alternative correlation structures (e.g., heterogeneous autoregressive, heterogeneous compound symmetry, autoregressive, or compound symmetry, in this order) will be considered. The Kenward-Roger approximation will be used to estimate the degrees of freedom. Comparison between ACP group and Sham group will be performed at a 2-sided 0.05 significance level. The difference between ACP group and Sham group (ACP – Sham) in the growth rate (slope) of the area of ellipsoid zone defect from Baseline through Month 18, i.e. the treatment effect, and the associated standard error and 95% confidence interval (CI) will be provided. The treatment effect estimate is taken to be the estimated regression coefficient for the interaction between treatment and time multiplied by 547.875 days (i.e. 18 months \times 30.4375 days/month).

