#### **11.4.3 Statistical Analyses**

All statistical analyses will be conducted by the study Sponsor or under the authority of the study Sponsor. The Sponsor and the subjects will remain masked to treatments until the end of the study, except if safety considerations justify breaking the code for individual subjects.

Primary endpoint will be analyzed using a mixed model for repeated measures (MMRM) with all available data, using response variable of the area of ellipsoid zone defect measured by en face SD-OCT over time up to Month 18 including baseline and post-baseline assessments. The MMRM will be used to assess the difference between the treatment groups in terms of the rate of change (slope) in the area of ellipsoid zone defect from Baseline through Month 18. The fixed effects will include treatment group (avacincaptad pegol or Sham), time, pooled geographic region (North America or Rest of World) and treatment by time interaction. Subject is the random effect with repeated measures.

The efficacy analysis will be conducted on all randomized subjects according to the intention-to-treat principle.

A Statistical Analysis Plan (SAP) will provide the details for the statistical analyses.

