4.4.2 Main Analytical Approach

For analyses of both secondary endpoints, the treatment effect will be estimated using MMRM with the following fixed effects: treatment group (ACP or Sham), visit (categorical variable), pooled geographic region (North America or Rest of World), treatment by visit interaction and baseline value of BCVA or photopic and/or mesopic macular sensitivity. The response variable will be the change from Baseline in BCVA or photopic and/or mesopic macular sensitivity measured by microperimetry at each scheduled post-baseline visit through Month 18. An unstructured (co)variance structure will be used to model the within-participant errors. The model will be fitted using REML estimation. If this analysis fails to converge, alternative correlation structures (e.g., heterogeneous autoregressive or heterogeneous compound symmetry, in this order) will be considered. The Kenward-Roger approximation will be used to estimate denominator degrees of freedom.

Statistical testing of the mean difference in change from Baseline in BCVA between ACP group and Sham group (defined as ACP minus Sham) at Month 18 from the MMRM will be performed at a 2-sided significance level of 5% only if the null hypothesis for the primary efficacy endpoint is rejected. The statistical testing of the difference for mean change from Baseline in photopic and/or mesopic macular sensitivity measured by microperimetry will be performed at a 2-sided significance level of 5% only if the null hypothesis for the primary efficacy endpoint and the secondary endpoint of change in BCVA at Month 18 are rejected, according to the fixed sequence procedure specified in Section 2.1.

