4.5 Supportive Endpoint(s) Analysis

The supportive endpoints are:

- Rate of change in the area of atrophic lesion (DDAF) measured by FAF from Baseline through Month 18
- Rate of change in the thickness of the outer nuclear layer measured by a horizontal scan through the foveal center using SD-OCT from Baseline through Month 18
- Rate of change in the square root transformed area of ellipsoid zone defect measured by en face SD-OCT from Baseline through Month 18
- Time to persistent vision loss (defined as BCVA loss ≥ 10 , 15 or 20 letters from Baseline at two or more consecutive visits through Month 18).
- Emergence of at least one new atrophic lesion (DDAF) measured by FAF through Month 18.

The supportive endpoints of the rate of change in the area of atrophic lesion (DDAF) measured by FAF from Baseline through Month 18, the rate of change in the thickness of the outer nuclear layer measured by a horizontal scan through the foveal center using SD-OCT from Baseline through Month 18, and the rate of change in the square root transformed area of ellipsoid zone defect measured by en face SD-OCT from Baseline through Month 18 will be analyzed similarly to the primary endpoint using the analysis method in Section 4.3.2. The MMRM model will include all observed outcomes for these endpoints at each scheduled visit from Baseline through Month 18. Fixed effects will include treatment group (ACP or Sham), time, pooled geographic region (North America or Rest of World), and treatment by time interaction. The random effects will be at the participant-level. The model will be fitted using REML estimation with unstructured (co)variance matrix. Comparison between ACP group and Sham group will be performed at a 2-sided 0.05 significance level. The difference between ACP group and Sham group (ACP – Sham) in the treatment effect, and the associated standard error and 95% CI will be provided.

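### The primary slope model gives each arm its own baseline mean and leaves baseline ellipsoid zone area unused, which costs precision if baseline area is correlated with slope

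*SAP*

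**What the plan says.** SAP 4.3.2 treats the baseline scan as an outcome: "The model will include all observed area of ellipsoid zone defect at each scheduled visit from Baseline through Month 18 in the response variable". The terms are given as "The fixed effects will include treatment group (ACP or Sham), time, pooled geographic region (North America or Rest of World", and the list closes with treatment-by-time. On covariance it says "The model will include an unstructured modeling of within-participant correlations, induced by random effects at the participant-level", and the reported effect is defined as follows: "The treatment effect estimate is taken to be the estimated regression coefficient for the interaction between treatment and time multiplied by 547.875 days". If the unstructured fit fails, the fallback list runs through heterogeneous structures to homogeneous autoregressive and compound symmetry.

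Protocol 11.4.3 begins its list the same way ("The fixed effects will include treatment group (avacincaptad pegol or Sham), time") and adds region and the interaction. The supportive slope models in SAP 4.5 share the form ("Fixed effects will include treatment group (ACP or Sham), time, pooled geographic region"). None of these has a baseline-area covariate, a baseline-by-time term, or a constraint that the arms start from one mean.

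The secondary models in SAP 4.4.2 do use baseline; their terms include "treatment by visit interaction and baseline value of BCVA or photopic and/or mesopic macular sensitivity".

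Minimization balances site and overall numbers only (SAP 1.3 and Appendix 1). The baseline table in SAP 4.2.3 names FAF imaging but no SD-OCT measure. Protocol 11.3.1 sets decision cut points at 0.1843 and 0.3577 slope SDs. Protocol 11.3.1 and SAP 4.9 both say that no natural history data exist for that SD.

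**The concern.** The sample size was set by feasible recruitment, so precision on the primary endpoint is scarce, and that endpoint gates both secondary tests (SAP 2.1). A free treatment main effect lets the fitted arms differ at time zero, although randomization makes their expected baseline means equal. With complete data the interaction coefficient is then the plain difference in mean individual slopes.

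If participants with larger defects progress at a different rate from those with smaller ones, in either direction, the baseline value explains part of the slope variation, and the plan does not use it. In a trial that happens to start unbalanced on lesion size, part of the observed slope difference would then reflect that imbalance. Allocation does not guard against this, and the variables named for the baseline table would not show it.

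**Working it through.** **Inputs from the documents.** 60 per arm (Protocol synopsis); scans read at Screening, Month 9 and Month 18 (Protocol section 7); cut point 0.3577 SD at one-sided 0.025 (Protocol 11.3.1). **Assumed:** r; baseline SD 4, slope SD 1 and residual SD 0.1 to 0.3, all in slope-SD units per 18 months; complete data; random intercept and slope.

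**1. The plan's own figure.** 1.96 × √(2/60) = 1.96 × 0.1826 = 0.3578, against 0.3577 stated. The cut point is therefore a normal-theory threshold on the unadjusted slope SD.

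**2. Level imbalance alone.** In simulated data, adding 3 mm² to one arm at every visit left the planned slope difference at 0.0873. The treatment main effect absorbs a pure shift in level.

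**3. Gain from a common baseline mean.** Let C be the covariance of a participant's fitted intercept and slope. With time scaled 0, 0.5, 1:
- C11 = (baseline SD)² + 0.8333 × (residual SD)²
- C12 = r × (baseline SD) × (slope SD) − (residual SD)²
- C22 = (slope SD)² + 2 × (residual SD)²

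The planned variance is (2/60) × C22. With equal baseline means it is (2/60) × C22 × (1 − C12²/(C11 × C22)).

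Example, r = 0.3 and residual SD 0.3: C11 = 16.075, C12 = 1.2 − 0.09 = 1.11, C22 = 1.18. The reduction is 1.2321/18.97 = 6.5%. With residual SD 0.1 it is 1.4161/16.33 = 8.7%.

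| r | Variance reduction, residual SD 0.3 to 0.1 | Reduction with no error (r²) | Participants for planned precision, 120(1 − r²) | Significance threshold, 0.3577√(1 − r²) |
|---|---|---|---|---|
| 0 | about 0 | 0 | 120 | 0.358 |
| 0.2 | 2.7-3.8% | 4% | 115 | 0.350 |
| 0.3 | 6.5-8.7% | 9% | 109 | 0.341 |
| 0.5 | 19.2-24.3% | 25% | 90 | 0.310 |

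Noisier scans shrink the gain. With residual SD at 0.4 of the slope SD (and slope SD half the baseline SD), it is 3.6% at r = 0.3 and 12.9% at r = 0.5.

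**4. Conditional effect of imbalance.** The expected shift per 1 SE of baseline imbalance is r × 0.1826 SD: 0.055 SD at r = 0.3 (15% of 0.3577) and 0.091 SD at r = 0.5 (26%).

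**5. Validity.** In 20,000 simulated null trials per setting, the mean slope difference was about 0 and two-sided error was 0.049 to 0.052 at intercept-slope correlations 0, 0.3 and 0.5. Among trials with baseline imbalance near 2 SE, error was 0.05, 0.08 and 0.13 respectively.

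**6. Fallback structures.** I computed the true variance when the working covariance is homogeneous (best-fitting compound symmetry or first-order autoregressive), with the step 3 settings and r from 0.2 to 0.5. The planned model's variance is unchanged. The common-baseline model's is higher by 2.7-6.4% (compound symmetry) or 2.8-8.2% (autoregressive). A pure level shift of one unit then moves its slope estimate by 0.014 to 0.025, against 0 for the planned model.

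**The case against.** The strongest reply is that the planned analysis is valid and the loss is hypothetical. Much of this stands. A reader might infer that any chance difference in lesion size biases the slope difference; step 2 shows that it does not. A reader might also infer that the primary test is invalid; step 5 shows no bias over randomization and no inflation of overall error. The excess rejection appears only after conditioning on a large imbalance together with a non-zero correlation.

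Nor do the documents show that larger defects progress faster. They give no baseline-slope correlation and not even a slope SD. At r of 0.1 to 0.2 the gain is at most 1 to 4%. At r = 0.5, a 2 SE imbalance would shift the estimate by 0.183 SD, more than the gap of 0.1734 between the two cut points. That pairs an assumed correlation with an uncommon imbalance and is not an expected result.

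Two further replies have some weight. The prespecified square-root analysis (SAP 4.5) would weaken a link between size and growth that comes purely from lesion geometry, but it is supportive only and has no baseline adjustment either. The secondary models analyze change from baseline, with baseline outside the response, so the difference in adjustment is not a contradiction. It does show that the plan accepts baseline adjustment in principle.

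Finally, deleting one term is not enough. Step 6 shows that the constraint does harm under two of the listed fallbacks, and step 3 shows that it separates the 0.3577 cut point from the significance threshold. Both objections are right, and the fix has to deal with them.

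**Conclusion.** The concern holds as one of efficiency and conditional accuracy, not validity. The primary model does not use a baseline measurement that the trial already collects. If baseline area is correlated with slope, a common baseline mean lowers the variance of the slope difference by roughly r squared: 0 at r = 0, about 3-4% at 0.2, 7-9% at 0.3 and 19-25% at 0.5. The sign of the correlation does not matter much (about 9% at −0.3).

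These figures assume complete data, small measurement error and a random intercept and slope. Which value of r applies cannot be read from the documents, so the benefit is a range that includes zero. Under the unstructured model, large-sample variance is not increased even at r = 0, so the change is close to free.

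**What to change.** Before unmasking:

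- **SAP 4.3.2 and Protocol 11.4.3.** Constrain both arms to a common baseline mean: drop the treatment main effect and keep time, region and treatment-by-time. Specify an unstructured random intercept and slope, with REML and Kenward-Roger as now. Keep the current model as a sensitivity analysis. SAP 4.3.3 and 4.3.4 refer back to this model and would inherit the change. Adding baseline area only as a main effect, with baseline still in the response, would not achieve this.
- **Fallback list.** If the unstructured model does not converge, use only the heterogeneous structures with the constraint, or revert to the model with the treatment main effect. Do not combine the constraint with homogeneous compound symmetry or autoregressive structures.
- **Protocol 11.3.1.** State that 0.1843 and 0.3577 are on the unadjusted slope-SD scale and that significance is judged by the model p-value.
- **SAP 4.2.3.** Add baseline ellipsoid zone defect area.

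The cost is one model term with its matching protocol text, a revised fallback list, one clarifying sentence and one table row. The small downside is reliance on the constraint when screening scans may precede randomization by up to 14 days, about 14/547.875 = 2.6% of the follow-up span. Placing the baseline scan 14 days early left the gain essentially unchanged (6.6% at r = 0.3, 19.5% at r = 0.5).

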Section # and Name	Description of Change	Brief Rationale
	
from Baseline through Month 18, when compared with Sham.
	

Section 11.4.3: Statistical Analyses
	
Revised primary endpoint analysis description as follows:  Primary endpoint will be analyzed using a mixed model for repeated measures (MMRM) with all available data, using response variable of the area of ellipsoid zone defect measured by en face SD-OCT over time up to Month 18 including baseline and post-baseline assessments. The MMRM will be used to assess the difference between the treatment groups in terms of the rate of change (slope) <del>of</del> in the area of ellipsoid zone defect from Baseline through Month 18 over time of 18 months. <del>For the model, The</del> fixed effects will include treatment group (avacincaptad pegol or Sham), time, pooled geographic region (North America or Rest of World) and treatment by time interaction.
	
 
• To clarify for readability.
 
• To parsimoniously adjust for the randomization stratification factor “Site” in the analysis.
 

Section 11.4.3: Statistical Analyses
	
Revised efficacy analysis population as follows:  The efficacy analysis will be conducted on all randomized <del>and treated</del> subjects according to the intention-to-treat principle.
	
To clarify that all randomized patients, irrespective of whether they were treated with study drug, will be included in the analysis, following the intention-to-treat principle.

Entire document
	
Administrative updates.
	
To provide updated information and clarification throughout the protocol.

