1.3 Randomization

Participants will be randomized in a 1:1 ratio to the following two treatment groups: ACP and Sham.

Participants will be centrally allocated to one of the two treatment groups by a dynamic minimization procedure (see Section 5.1 Appendix 1 for details). Randomization will be stratified by site and performed using an IRT system based on the stratification information to randomize each participant and assign a treatment group. Details of the randomization procedure can be found in Appendix 1.

All participants will be treated as follows:

Induction Phase: Administered starting on Day 1, 14 days apart for a total of 6 administrations (Day 1 – Month 2):

- ACP 2mg/eye or Sham

Maintenance Phase: Administered monthly (Month 3 – Month 17):

- ACP group continued with ACP 4 mg/eye (administered as two injections of ACP 2 mg)
- Sham group continued with Sham + Sham to maintain the masking

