Time to persistent vision loss is defined for each participant as the first study day (in months) where the participant experiences a BCVA loss ≥ 10 , 15 or 20 letters from Baseline at two or more consecutive visits through Month 18. Participants without a vision loss event have their time to event censored at the last assessment of BCVA prior to the end of the study, or at 0.03285 months (i.e. day 1) if no post-baseline BCVA assessments are available. The hazard ratio for ACP vs. Sham on time to persistent vision loss, along with its corresponding 95% CI, will be calculated using a stratified Cox proportional hazards regression model with

pooled geographic region (North America or Rest of World) as the stratification factor. The two-sided p-value will be derived using the stratified log-rank test with pooled geographic region as the stratification factor. The 5th percentile and median time to the first occurrence of persistent vision loss will be analysed using the Kaplan-Meier method without stratification. Additionally, the event rate at Month 6, 9, 12, 15 and 18, and corresponding 95% CIs will be estimated using the Kaplan-Meier method without stratification and Greenwood formula with complementary log-log transformation.

For the emergence of at least one new atrophic lesion (DDAF) through Month 18, participants who do not have any atrophic lesion (DDAF) assessments through Month 18 will be excluded from the analysis. A dichotomized response (yes or no new atrophic lesion) will be evaluated and tested using Cochran-Mantel-Haenszel χ^2 test for risk difference between ACP and Sham adjusting for the stratification factor of pooled geographic region (North America or Rest of World). The odds ratio and its corresponding 95% CI will be reported for ACP vs. Sham.

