4.10.3 Pooling Algorithm

For analysis purposes all participants will be pooled by geographic region, with this same variable then used as a fixed effect in any statistical modeling. The pooling will occur according to the following rule:

Participants will be grouped into their geographic regions defined by the categories North America and Rest of World.

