5 SUPPORTING DOCUMENTATION

5.1 Appendix 1 Randomization Approach

The dynamic minimization algorithm described in Pocock and Simon (Pocock et al. 1975) was used to allocate patients to either ACP or Sham in this study. This procedure consists of two steps. First, the level of balance in treatment assignments within 1) the strata of randomization stratification factors (i.e. site) and 2) the overall population are determined for the settings where a new participant is assigned to ACP or Sham. Then, the treatment assignment that would cause the least imbalance is attributed higher probability when assigning the actual treatment assignment to the new participant. Note that this allocation scheme helps balance the treatment assignment while maintaining a random component.

Imbalance measures

Let X_{jk} be the number of participants already assigned to treatment k ($k = \text{ACP, Sham}$) within site j ($j = 1, 2, \dots, S$) as the new participant to be assigned. That is, X_{jACP} and X_{jSham} are the number of participants already assigned to receive ACP and Sham within site j , respectively. Additionally, let Y_{ACP} and Y_{Sham} be the total number of participants already assigned to ACP and Sham across all sites, respectively.

Suppose a new participant is enrolled at Site j . Then, the imbalance in treatment assignments at the site-level is defined by:

$$D_{ACP} = |X_{jACP} - X_{jSham} + 1| \text{ if the new participant is assigned to ACP or}$$

$$D_{Sham} = |X_{jACP} - X_{jSham} - 1| \text{ if the new participant is assigned to Sham}$$

Where $|a|$ is the absolute value of a . Similarly, the imbalance in treatment assignments in the overall population is defined by:

$$T_{ACP} = |Y_{ACP} - Y_{Sham} + 1| \text{ if the new participant is assigned to ACP or}$$

$$T_{Sham} = |Y_{ACP} - Y_{Sham} - 1| \text{ if the new participant is assigned to Sham}$$

The overall imbalance measure is defined by:

$$I_t = W_1 D_t + W_2 T_t \text{ (} t = \text{ACP or Sham)}$$

Where W_1 and W_2 are positive weights that sum to one and are prespecified before the second participant has been randomized. The weights will only be made available to the broader study team after database lock.

Allocation

The first participant will be assigned to ACP or Sham with equal chance. Then, for each subsequent participant, the participant will be assigned to ACP with probability p or to Sham with probability $1 - p$, based on the following rules:

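### Pooled region enters the slope models only as a main effect, so it barely touches the tested treatment-by-time term; if region predicts progression and random slopes are fitted, the primary interval is somewhat too wide, and the visit-based secondary models share the weakness

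*SAP*

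**What the plan says.** SAP 4.3.2 models the area of ellipsoid zone defect at every visit, baseline included, with time continuous. It lists its terms thus: "fixed effects will include treatment group (ACP or Sham), time, pooled geographic region (North America or Rest of World), and treatment by time interaction". What is tested is stated directly: "The treatment effect estimate is taken to be the estimated regression coefficient for the interaction between treatment and time", scaled to 18 months. Protocol 11.4.3 has the same terms, ending with "pooled geographic region (North America or Rest of World) and treatment by time interaction". SAP 4.5 repeats them for the three supportive rate-of-change endpoints (DDAF area, outer nuclear layer thickness, square-root ellipsoid zone area). None of these models has a region-by-time term.

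The reason for including region is in the Amendment C table of changes, in the entry for protocol 11.4.3: "To parsimoniously adjust for the randomization stratification factor" Site. That entry explains the current model. On allocation, SAP 1.3 says: "Randomization will be stratified by site and performed using an IRT system". SAP Appendix 1 gives the minimisation rule (0.8/0.2 biased coin). SAP 4.10.3 defines two regions, "with this same variable then used as a fixed effect in any statistical modeling".

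The secondary models in SAP 4.4.2 use change from baseline, with treatment, categorical visit, treatment-by-visit, baseline value and region. They have no region-by-visit term. The imputation model in SAP 4.3.3, carried into 4.4.3, also has region as a main effect only.

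**The concern.** When the response is a level measured over time and the tested parameter is a difference in slopes, a covariate's main effect adjusts the wrong quantity. To reach the slope difference, region must be allowed to have its own slope.

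This matters because allocation is minimised on site, and sites nest within regions, so region is largely balanced between arms. A model that leaves the regional slope difference in the residual then reports an SE larger than the estimate's real spread. The cost is precision, on the endpoint that opens the fixed testing sequence in SAP 2.1. Under a visit-based model, one constant regional offset meets a similar problem if the regions drift apart over time.

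**Working it through.** **Inputs.** From the documents: 120 participants, 60 per arm; scans read at Screening, Month 9 and Month 18 (protocol section 7); the Appendix 1 minimisation rule. Not in the documents, hence assumed: North America share p, regional slope difference d, scan-error SD σ, number of sites, minimisation weights. Slope SD within region is set to 1 per 18 months, because protocol 11.3.1 and SAP 4.9 say that none is available.

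**1. The plan's own figure.** Protocol 11.3.1 puts significance at 0.3577 slope SD. 1.95996 × √(2/60) = 0.3578, so it reproduces (the stated cut-off has one-sided error 0.02504).

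**2. Does the region main effect reach the slope?** With complete scans at common times, each participant reduces to an intercept and a slope. The slope equation contains treatment only; the intercept equation contains treatment and region. Since the slope regressors are a subset of the intercept regressors, generalised least squares returns the plain difference in mean slopes. Region drops out.

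REML fits with random intercept and slope in six simulated trials (d = 1) confirmed it. In one of them:

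| Model | Estimate | SE |
|---|---|---|
| No region | −0.1362 | 0.2234 |
| Region main effect | −0.1362 | 0.2234 |
| Region × time | −0.1362 | 0.2042 |

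Across the six, region × time cut the SE by about 6–9%. With 15% dropout and jittered visit times, the main effect moved the SE by at most 0.0007 and never reduced it.

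**3. How much wider is the reported SE?** An individual slope from scans at 0, 0.5 and 1 (in units of 18 months) has error variance σ²/0.5 = 2σ². Omitting region × time adds p(1−p)d² to the slope variance, so

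SE ratio = √[1 + p(1−p)d² / (1 + 2σ²)].

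| p, σ | d = 0.3 | d = 0.6 | d = 1 |
|---|---|---|---|
| 0.6, 0 | 1.011 | 1.042 | 1.114 |
| 0.6, 0.3 | 1.009 | 1.036 | 1.097 |
| 0.6, 0.6 | 1.006 | 1.025 | 1.067 |
| 0.8, 0.6 | 1.004 | 1.017 | 1.045 |

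Simulation under the Appendix 1 rule with 25 sites, which includes the cost of the extra parameter, gave 0.3–1.0%, 1.5–4.1% and 4.4–11.4%.

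**4. Calibration under minimisation** (p = 0.5, 30 sites, equal weights, σ = 0):

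| d | Model SE | True SD | Coverage |
|---|---|---|---|
| 0 | 0.182 | 0.182 | 95.0% |
| 0.5 | 0.188 | 0.185 | 95.4% |
| 1 | 0.204 | 0.192 | 96.4% |

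With region × time the SE stays at 0.182–0.183 and coverage at about 95%. Under simple randomisation the plan's model covers 95.3% at d = 1, so the over-coverage comes from the balanced allocation. Type I error of the plan's model was 3.0–5.1% over 39 settings.

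**5. The models in SAP 4.4.2.** Let δ be the regional difference by visit (linear, reaching d at Month 18) and Σ the covariance of the changes. The single offset converges to g = (1′Σ⁻¹δ)/(1′Σ⁻¹1), and the Month 18 SE exceeds the region × visit SE by √[1 + p(1−p)(d−g)²/Σ₁₈] − 1, where Σ₁₈ is the Month 18 variance. I took p = 0.6 and σ = 0.3 or 0.6.

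- BCVA, 21 post-baseline visits, baseline the mean of two values (SAP 4.1): g captures 2% (σ = 0.3) or 7% (σ = 0.6) of d, because the precise early visits dominate. At σ = 0.3, Σ₁₈ = 1 + 0.09 + 0.045 = 1.135, and at d = 1 the ratio is √(1 + 0.24 × 0.98²/1.135) = 1.097. The full range is 2.4–3.6% at d = 0.6 and 6.5–9.7% at d = 1.
- Microperimetry, two visits, one baseline value: g captures 31% or 56%, leaving 0.5–1.7% at d = 0.6 and 1.4–4.7% at d = 1.

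**6. The condition on random slopes.** With a random intercept only, the model SE is √[(0.5 + 2σ²)/30]. At σ = 0.3 and d = 0 this is √(0.68/30) = 0.151, against a true SD of √(1.18/30) = 0.198, and coverage is about 86%. The direction of the error would then reverse.

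**The case against.** **The plan does what it says.** Amendment C promises only a parsimonious adjustment, SAP 4.10.3 defines it as using region as a fixed effect, and no passage promises to adjust the slope. This stands: the plan breaks no rule of its own. What remains is that the chosen term has almost no effect on the contrast it was added to serve.

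**Nothing shows that region predicts progression.** Also true. Eligibility is confirmed genetically and by a reading centre. If d is 0 nothing is lost, and at 0.3 SD the loss is at most about 1% of the SE.

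**The re-randomization test in SAP 4.3.4 already deals with it.** Largely true for the p-value. At an assumed effect of 0.5 slope SD and σ = 0.3, power for the plan's model, its re-randomization test and region × time is 66.5/68.4/69.0% at d = 0.6 and 62.5/66.2/69.2% at d = 1. With d = 0.6 plus site-level slope variation (SD 0.4) it is 62.2/67.0/64.9%, so there the existing test does better than the added term. But it is a sensitivity analysis and leaves the reported SE and CI unchanged.

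**The direction depends on the covariance model.** This stands. SAP 4.3.2 implies random slopes through its unstructured correlation but does not list the random effects, protocol 11.4.3 names only subject, and the last fallback is compound symmetry.

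**Conclusion.** The point holds as a low-severity improvement. In the slope models, region has essentially no influence on the tested coefficient or its SE. With participant-level random slopes or an equivalent covariance, and if region predicts progression, the primary SE and CI are too wide by about 0.3–1%, 1.5–4% or 4–11% at regional slope differences of 0.3, 0.6 or 1 SD. The region split, scan error, number of sites and weights behind these ranges are assumed as well.

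Three stronger readings should be resisted:

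- A reader might infer that the primary estimate is biased or its type I error inflated. Under the random-slope reading neither is so; the test is slightly conservative.
- A reader might infer that only the slope models are affected, because 4.4.2 analyses change from baseline. It has no region-by-visit term, so BCVA at Month 18 is left almost unadjusted and microperimetry partly so. The stratified Cox, log-rank and Cochran-Mantel-Haenszel analyses in 4.5 do carry region to the tested contrast, as does the Month 18 ANCOVA step in 4.4.3.
- A reader might infer that the interval is too wide whatever covariance is fitted. With a random intercept only it would be too narrow, and a region term does not cure that.

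**What to change.** Before unmasking:

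- Add region × time to the slope models in SAP 4.3.2 and 4.5 and in protocol 11.4.3, keeping treatment × time as the tested term. SAP 4.3.4 follows, since it uses the 4.3.2 model.
- Add region × visit to the models in SAP 4.4.2 and to the imputation models in 4.3.3 and 4.4.3.
- If the primary model must stay as written, prespecify the region × time version as a sensitivity analysis and say that region adjusts only the level of the area.

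No new data are needed. The slope models gain one parameter, and the visit models one per additional visit (20 for BCVA with 21 visits, one for microperimetry). If region does not predict slope, the primary SE rises by about 0.1–0.3%; that figure was not worked out for the visit models. The change adjusts for region, not for site itself, so the re-randomization test should stay.
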